8 HUMAN SUBJECTS CONSIDERATIONS

8.1 Ethical Review

This protocol and the template informed consent form contained in Appendix II — and any subsequent modifications — will be reviewed and approved by the HPTN Protocol Review Committee and DAIDS Prevention Science Review Committee with respect to scientific content and compliance with all applicable research and human subjects regulations.

The protocol, site-specific informed consent form, participant education, outreach, and recruitment materials, and other requested documents — and any subsequent modifications — also will be reviewed and approved by the IRB responsible for oversight of research conducted at the study site. Subsequent to initial review and approval, the local IRB will review the protocol at least annually. The Investigator will make safety and progress reports to the IRB at least annually, and within three months of study termination or completion. These reports will include the total number of participants enrolled in the study, the number of participants who completed the study, all changes in the research activity, and all unanticipated problems involving risks to human subjects or others.

8.2 Informed Consent

Written informed consent will be obtained from each study participant. The study site is responsible for developing a study informed consent form for local use, based on the template in Appendix II, that describes the purpose of the study, the procedures to be followed, and the risks and benefits of participation, in accordance with applicable regulations. The DAIDS ROC will review all site-specific informed consent forms and approve them for use according to DAIDS policies; study site staff may not begin obtaining informed consent from study participants until after receiving ROC approval of the forms, in the form of confirmed "site registration" to begin study operations.

Participants will be provided with a copy of their informed consent forms if they are willing to receive them. Study staff will document the informed consent process as described in the study-specific procedures manual.

8.3 Risks

Based on the results of prior Phase I studies conducted among HIV-uninfected men, it is possible that the study gels could cause genital itching, tingling, irritation, dryness, discoloration, or flaking of the dried gel. It also is possible that the gels could cause burning, pain, blisters, ulcers, sores, or other irritation of the penis. These effects are sometimes seen when men apply other gels to the penis. Also, these effects were seen in some women who tested the gels in the vagina. Some women also experienced difficulty urinating, pain when urinating, vaginal bleeding, abdominal pain, nausea, and diarrhea. Other unknown effects and risks could occur.

Also, it is possible that participants could experience social harm as a result of taking part in this study. For example, others could learn of participants' involvement in this study and infer that they are HIV-infected. Because of this, participants could be treated unfairly or discriminated against. Participants could experience embarrassment if others were to see and recognize digital photographs of their penis.

8.4 Benefits

There are no direct benefits to participants in this study. However, participants and others may benefit in the future from information learned from this study. Specifically, information learned in this study may lead to the development of a safe and effective microbicide that prevents sexual transmission of HIV.

8.5 Confidentiality

All study-related information will be stored securely at the study site. All participant information will be stored in locked file cabinets in areas with access limited to study staff. All laboratory specimens, reports, photographs, study data collection, process, and administrative forms will be identified by a coded number only to maintain participant confidentiality. All records that contain names or other personal identifiers, such as locator forms and informed consent forms, will be stored separately from study records identified by code number. All local databases will be secured with password-protected access systems. Forms, lists, logbooks, appointment books, and any other listings that link participant ID numbers to other identifying information will be stored in a separate, locked file in an area with limited access.

Participants' study information will not be released without the written permission of the participant, except as necessary for monitoring by NIAID and/or its contractors (e.g., the DAIDS monitoring contractor), the manufacturers of the study products, representatives of the HPTN Coordinating and Operations Center (CORE) and/or SDMC, and the FDA and other regulatory authorities.

8.6 Incentives

Participants will be compensated for their time and effort in this study. Pending IRB approval, they will receive \$25 for each scheduled study visit.

8.7 Communicable Disease Reporting Requirements

Study staff will report communicable diseases identified among study participants as required by law. Participants will be made aware of all applicable reporting requirements during the study informed consent process.

8.8 Study Discontinuation

As noted in Section 7.5, accrual into this study will be suspended if two or more grade 3 or higher AEs (as defined by the DAIDS Standard Toxicity Tables) judged possibly, probably, or definitely related to product use are observed across at least two study participants. The study team then will review all pertinent data and determine whether to continue accrual and product use. A decision to stop the trial may be made by the study team at this time, or at any such time that the team agrees that an unacceptable type and/or frequency of AEs has been observed.

The study also may be discontinued at any time by NIAID, the HPTN, the manufacturers of the study products, and/or the FDA or other regulatory authorities.

9 LABORATORY SPECIMENS AND BIOHAZARD CONTAINMENT

As the transmission of HIV and other blood-borne pathogens can occur through contact with contaminated needles, blood, and blood products, appropriate blood and secretion precautions will be employed by all personnel in the drawing of blood and shipping and handling of all specimens for this study, as currently recommended by the US Centers for Disease Control and Prevention.

10 ADMINISTRATIVE PROCEDURES

10.1 Study Coordination

NIAID will hold the Investigational New Drug (IND) application for this study. Copies of all regulatory documents submitted to this IND by NIAID will be forwarded to ReProtect and Interneuron Pharmaceuticals, for cross-referencing with the companies' other INDs for the study products. Assignment of all sponsor responsibilities for this study will be specified in a Clinical Trial Agreement executed between NIAID and each company.

Study implementation will be directed by this protocol as well as a study-specific procedures (SSP) manual. The SSP manual will outline procedures for conducting study visits; data and forms processing; AE assessment, management and reporting; dispensing study products and documenting product accountability; and other study operations.

Study case report forms will be developed by the study team and HPTN SDMC. Data will be transferred to the HPTN SDMC, entered, and cleaned using the SDMC DataFax data management system. Quality control reports and queries will be routinely sent back to the site for verification and resolution.

Close cooperation between the study Investigator, NIAID Medical Officer, Protocol Coordinator, Biostatistician, Data Managers, and other study team members will be necessary in order to track study progress, respond to queries about proper study implementation, and address other issues in a timely manner. Rates of accrual, adherence, follow-up, and AE incidence will be monitored closely by the study team. These rates also will be evaluated by representatives of the HPTN CORE and SDMC on a regular basis. A Protocol Clarification Team — comprised on the Protocol Chair, Medical Officer, and Biostatistician — will address issues related to study eligibility and AE management and reporting as needed to assure consistent case management, documentation, and information sharing.

10.2 Study Monitoring

On-site study monitoring will be performed in accordance with DAIDS policies. Study monitors will visit the site to verify compliance with human subjects and other research regulations and guidelines, assess adherence to the study protocol and study-specific procedures manual, and confirm the quality and accuracy of information collected at the study site and entered into the study database. The Investigator will allow study monitors to inspect study facilities and documentation (e.g., informed consent forms, clinic and laboratory records, other source documents, case report forms, product accountability forms), as well as observe the performance of study procedures. The Investigator also will allow inspection of all study-related documentation by authorized representatives of the HPTN CORE, SDMC, NIAID, ReProtect, Interneuron Pharmaceuticals, FDA, and other regulatory authorities. A site visit log will be maintained at the study site to document all visits.

10.3 Protocol Compliance

The study will be conducted in full compliance with the protocol. The protocol will not be amended without prior written approval by the Protocol Chair and NIAID Medical Officer. All protocol amendments must be submitted to and approved by the relevant IRB(s) and the DAIDS ROC prior to implementing the amendment.

10.4 Investigator's Records

The Investigator will maintain, and store in a secure manner, complete, accurate, and current study records throughout the study. In accordance with Federal regulations, for each of the two investigational products tested, the Investigator will retain all study records for at least two years following the date of marketing approval for the study product for the indication in which it was studied. If no marketing application is filed, or if the application is not approved, the records must be retained for two years after the FDA is notified that the IND is discontinued. Study records include administrative documentation — including site registration documents and all reports and correspondence relating to the study — as well as documentation related to each participant screened and/or enrolled in the study — including informed consent forms, locator forms, case report forms, notations of all contacts with the participant, and all other source documents.

10.5 Use of Information and Publications

Publication of the results of this study will be governed by DAIDS and HPTN policies. Any presentation, abstract, or manuscript will be made available by the Investigator to the HPTN Manuscript Review Committee, DAIDS, and the study product manufacturers for review prior to submission.

12 PROTOCOL MODIFICATIONS

The table below describes the history of modifications to this protocol.

Date	Version	Modifications	
9 March 2001	1.0	NA (original version of protocol)	
11 July 2001	1.0	Clarification #1:	
		Add IND number.	
		Clarify SAE reporting requirements to correspond with updated	
		DAIDS SAE Reporting Manual for the HPTN.	
20 August 2001	2.0	Amendment #1:	
		 Incorporate Clarification #1. 	
		Clarify primary endpoints.	
		Update safety information.	
		 Revise exclusion criteria to clarify that dermatologic conditions are exclusionary only if specific to the penis. 	
		 Add use of digital photography in conjunction with genital exams. 	
		 Add protocol Section 12, "Protocol Modifications." 	
		 Update protocol version number, date, and table of contents. 	

Appendix I

HPTN 032 Male Tolerance Study of BufferGel and PRO 2000/5 Gel (P)

SCHEDULE OF EVENTS

	Screening & Enrollment Visit	Follow-Up Evaluation Visit	Post-Washout/ Pre-Product Use Visits
Procedure	(Day 0)	(Days 7, 21, and 35)	(Days 14 and 28)
Obtain informed consent	Χ		
Collect demographic information	Х		
Collect/update locator information	Χ	X	Х
Obtain medical history	Х	X	X
Assess vital signs and perform	Х		
directed physical exam			
Perform genital exam and urine	Х	X	X
leukocyte esterase test/take digital			
photograph of any observed			
abnormality and of normal area(s) if			
needed for clinical decision-making			
and/or documentation purposes			
Determine eligibility	Χ		X
Obtain random assignment	Χ		
Provide study product, diary, and	Χ		Х
instructions			
Administer acceptability assessment		Х	
Complete and submit data collection	Х	X	X
forms			

Appendix III

HPTN 032 Male Tolerance Study of BufferGel and PRO 2000/5 Gel (P)

ASSESSMENT, FOLLOW-UP, AND TREATMENT OF SIGNS AND SYMPTOMS

Condition	Product Use	Further Evaluation	Follow-up
Irritative symptoms	If no signs are observed	None	Re-examine within 3 days if
(itching, burning, pain, etc.)	on exam or urine test,		symptoms persist.
	continue current product		
	use; otherwise follow		
	guidelines for observed		
	signs.		
Questionable Erythema	Continue current product	None.	Re-examine at end of product use
	use.		period (at next scheduled Post-Use Evaluation Visit). Consider for
			crossover to next product.
Definite Erythema	Discontinue current	None.	Re-examine within 3 days.
Bernite Liyuenia	product use.	rvone.	Consider for crossover to next
	product use.		product.
Erythema and Induration	Discontinue current	None.	Re-examine within 3 days.
	product use.	1,01101	Consider for crossover to next
			product.
Vesiculation	Discontinue product use.	None.	Re-examine within 3 days.
			Follow-up to resolution then
			discontinue from study.
Bullous Reaction	Discontinue product use.	None.	Re-examine within 3 days.
			Follow-up to resolution then
			discontinue from study.
Ulceration	Discontinue product use.	Culture and DFA for	Re-examine within 3 days. Treat
		herpes simplex virus 2; evaluate for other causes	infection (if diagnosed) with
		(e.g., syphilis, chancroid)	appropriate antibiotic therapy. Follow-up to resolution then
		if suspected based on	discontinue from study.
		clinical judgement.	discontinue from study.
Other Epithelial Change	Continue or discontinue	None.	Re-examine within 3 days.
guner Zpranemar emange	current product use	T toller	Consider for crossover to next
	based on clinical		product.
	judgement.		•
Positive urine LE	Discontinue current	Urine culture and urine	Re-evaluate in 5-7 days, when
(>trace)	product use.	LCR for gonorrhea and	urine test results are available.
		chlamydia.	Treat infection (if diagnosed) with
			appropriate antibiotic therapy. If
			STD is diagnosed, follow to
			resolution, then discontinue from study. Otherwise consider for
			crossover to next product.
Confirmed STD	Discontinue product use.	None.	Treat with appropriate antibiotic
	2 iscontinue product disc.	Tione.	therapy. Follow to resolution, then
			discontinue from study.

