Particularly in light of the most recent findings with respect to the effects of nonoxynol-9 products, increasing attention has been given to developing non-detergent topical microbicides to prevent HIV infection. Two such products are BufferGel, developed by Reprotect, LLC, and PRO 2000/5 Gel (P), developed by Procept, Inc. and acquired recently by Interneuron Pharmaceuticals, Inc. BufferGel is designed to protect against HIV infection by maintaining the normally acidic pH of the vagina in the presence of ejaculate. PRO 2000/5 Gel (P) is designed to protect against HIV infection by inhibiting viral entry into susceptible cells.

BufferGel and PRO 2000/5 Gel (P) currently are not approved by the US Food and Drug Administration (FDA) for any use. However, both products have undergone extensive pre-clinical testing, both have been shown to inhibit/inactivate HIV in vitro, and both are compatible with condoms. Both products also have undergone clinical testing in Phase I trials among healthy HIV-uninfected sexually abstinent and sexually active women. PRO 2000/5 Gel (P) also has been tested among HIV-infected women. In these studies, the products were shown to be safe and acceptable for vaginal use [10-13].

Phase I trials also have been conducted to assess the safety of BufferGel and PRO 2000/5 Gel (P) on the penile epithelium and urethral mucosa. In one trial, HIV-uninfected men applied either PRO 2000/5 Gel (P) (n=24) or a gel containing the inactive ingredients of PRO 2000/5 Gel (P) (n=12) to the penis for seven consecutive days. About one in three users of the active gel and one in four users of the inactive gel reported mild symptoms of genital itching, tingling, irritation, dryness, discoloration, or flaking of the dried gel. In a similar trial comparing BufferGel and K-Y Jelly (a marketed sexual lubricant), about one in eight users of BufferGel and one in six users of K-Y Jelly reported similar symptoms.

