3.4 Participant Withdrawal

Once a participant has enrolled in the study, the study site will make every reasonable effort to retain him for the entire five-week study period. Given the small study sample size, and the importance of ascertaining all safety outcomes among study participants, 100 percent retention of enrolled participants is targeted. Study site staff are responsible for developing and implementing local standard operating procedures to achieve complete follow-up.

However, participants may withdraw from the study for any reason at any time. The Investigator also may withdraw participants from the study in order to protect their safety (e.g., due to intolerance of the study products or development or exacerbation of a concomitant medical condition) and/or if they are unwilling or unable to comply with required study procedures. In particular, participants who experience vesiculation, bullous reaction, or ulceration, or are diagnosed with a confirmed STD, will be followed until the condition resolves and then will be withdrawn from the study (see Appendix III). Participants who voluntarily withdraw from the study, are withdrawn by the Investigator, or are not adherent to the study product application regimen, as defined in Section 4.5, will be replaced.

Participants also may be withdrawn if the study sponsor or regulatory authorities terminate the study prior to its planned end date.

Every reasonable effort will be made to complete a final evaluation of participants who terminate from the study prior to Day 35, and study staff will record the reason(s) for all withdrawals from the study in participants' study records.

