4.5 Adherence Assessment

Participants will record in their study diaries the date and time of each product application, as well as the date and time at which each application is washed off. The diaries also will collect information on participant compliance with other protocol requirements (e.g., abstinence from sexual intercourse). Participants will return all used and unused product syringes to the study site at their Day 7, 21, and 35 visits. At these visits, Study staff will assess adherence with the study product use regimen by reviewing the study diaries, counting the number of used and unused syringes, and discussing participants' experiences.

Application of all three study products on all seven consecutive assigned nights will be targeted, however lapses of product use on one or two assigned nights will be accommodated, as follows:

Participants who miss one application will be instructed to complete the remaining application on the night following the seventh assigned night, and then to present for their post-use evaluation visit. In such cases, participants will have completed at least one consecutive nightly application immediately prior to the evaluation.

Participants who miss two applications will be instructed to complete two applications on the two consecutive nights following the seventh assigned night, and then to present for their post-use evaluation visit. In such cases, participants will have completed at least two consecutive nightly applications immediately prior to the evaluation.

Note: In some cases, this scenario may result in participants completing a total of eight product applications; additional product supplies will be provided to participants as needed.

Participants who complete seven applications of each product on seven consecutive nights, or adhere to the two scenarios just described, will be considered "adherent" to the product use regimen. In addition to the above, participants who experience an adverse event (AE) that requires product discontinuation (see Appendix III), but apply study products on all nights prior to experiencing the AE also will be considered "adherent" to the product use regimen.

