4.6 Toxicity Management

Participants will be instructed to report all AEs to study staff at the time of AE onset. Participants who report AEs deemed by the study clinician — based on the participant's description — to be associated with use of study products will be instructed to wash off the product with plain warm water and to present to the study site for an in-person evaluation (except in potential emergency situations, in which participants will be instructed to present to an emergency room). Based on the results of this evaluation, the Investigator will recommend either continuation or discontinuation of product use, consistent with the criteria in Appendix III. The investigator also may prescribe or recommend the use of medications or other preparations to treat the AE.

Participants who discontinue use of one study product due to an AE — other than vesiculation, bullous reaction, ulceration, or confirmed STD — will not routinely be withdrawn from the study. In consultation with the Protocol Clarifications Team (see Section 10.1) the Investigator will judge whether the participant should continue product use and/or be "crossed over" and, following a washout period, begin use of the other study product(s). Participants who experience vesiculation, bullous reaction, or ulceration, or are diagnosed with a confirmed STD, will be followed until the condition resolves and then will be withdrawn from the study. All AEs will be followed and reported as described in Section 6.

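### Appendix III directs continued dosing for sign-free irritative symptoms of any grade, and no section sets a symptom grade at which such a man should stop

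*Protocol*

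**What the plan says.** Appendix III lists conditions and what to do about product use for each. The irritative-symptoms row describes the condition by type only and gives no severity. Its instruction begins "If no signs are observed" (on exam or urine test) and directs that the current product be continued; if signs are present, the row for those signs applies. No further evaluation is asked for, and the man is re-examined within 3 days only if symptoms persist. The row for other epithelial change is worded differently: "Continue or discontinue", according to clinical judgement.

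Section 4.6 makes the table the reference for the decision: "the Investigator will recommend either continuation or discontinuation of product use, consistent with the criteria in Appendix III". Section 6 repeats this and has every adverse event graded on the DAIDS table. The one action rule based on those grades is at study level: Sections 7.5 and 8.8 suspend accrual after two or more product-related events of grade 3 or higher across at least two men.

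Two other sections bear on a man who stops. Section 3.4 lets the Investigator withdraw a man for his safety, for example "due to intolerance of the study products". Section 4.5 counts as adherent "participants who experience an adverse event (AE) that requires product discontinuation (see Appendix III"), provided he applied the gel on all nights before the event. Section 4.6 says that men who discontinue one product for an adverse event, outside four listed conditions, are not routinely withdrawn.

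**The concern.** Urethral pain, urethral burning and penile itching are primary endpoints (Section 7.1.1), and they can occur with nothing to see on a visual exam and no positive leukocyte esterase test. For such a man the table gives one direction, to keep applying the gel, whether the symptom is mild or severe. Obvious redness without pain stops the product; severe pain without redness does not. If he is re-examined and still has no sign, he returns to the same row.

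What is at stake is avoidable exposure of an individual to a gel suspected of causing a severe symptom. A secondary matter is his status if he does stop. The Section 4.5 exemption refers to a discontinuation that is required and points to Appendix III, which requires none for sign-free symptoms. Section 4.5 also says that non-adherent men are withdrawn and replaced, so his remaining product periods could be lost.

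**Working it through.** **1. The plan's own figures.** Section 7.2 states 91% (n = 12, rate 30%) and 97% (n = 24, rate 20%) for two or more events. The exact binomial gives 0.915 and 0.967, so both reproduce. The point does not depend on them and does not change them.

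**2. Is there an individual stop that reaches sign-free symptoms?**

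| Provision | Basis for action | Reaches a severe, sign-free symptom? |
|---|---|---|
| Appendix III, irritative symptoms | Symptom type, no grade | Yes, and directs continuation |
| Appendix III, definite erythema and worse | Visible sign | No |
| Appendix III, positive urine test or confirmed STD | Test or diagnosis | No |
| Section 3.4, withdrawal for safety | Investigator's discretion | Yes, optional, no threshold; ends participation |
| Section 4.6, wash-off and in-person evaluation | Event deemed product-associated | Yes, but the recommendation that follows is tied to Appendix III |
| Section 6, severity | Place of evaluation (site or emergency room) | Does not decide product use |
| Sections 7.5 and 8.8 | Related grade 3+ events in at least two men | Accrual only; a single man does not trigger it |

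As an illustration of the last row, assume a fraction p of 24 men have a related grade 3+ event. The chance that exactly one man is affected, so that the rule is not met, is 24 × p × (1 − p)^23. This gives 0.30, 0.37, 0.21 and 0.03 for p = 2%, 5%, 10% and 20%. At the lower rates a lone case is a realistic outcome. These rates are assumed; the protocol gives none.

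**3. How often the row might be used.** Section 1.1 reports symptoms in about one in three users of PRO 2000 in an earlier trial in men, and in the other trial "about one in eight users of BufferGel and one in six users of K-Y Jelly reported similar symptoms". With 24 men per gel:

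- PRO 2000: 24 × 1/3 = 8
- BufferGel: 24 × 1/8 = 3
- K-Y Jelly: 24 × 1/6 = 4
- Total: 15 of 24 × 3 = 72 product-use periods, or 20.8%

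This assumes that the rates carry over from HIV-uninfected men. It is a ceiling for this row, because the protocol does not say how many of those men were sign-free and the symptoms counted include dryness, discoloration and flaking. The PRO 2000 users "reported mild symptoms of genital itching, tingling, irritation, dryness, discoloration, or flaking of the dried gel", so continuing is right for nearly all of them.

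**4. How many might be severe.** The protocol gives no grade 3 share. Assumed shares of 0%, 5% and 10% give 15 × 0 = 0, 15 × 0.05 = 0.75 and 15 × 0.10 = 1.5 periods in the whole study.

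**5. Exposure per case.** With one dose a night and re-examination within 3 days, at most 3 further doses before the first re-examination. This does not bound total exposure, since re-examination can lead back to the same row.

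**6. Adherence if he stops.** Missed nights after k doses are 7 − k. For k = 1, 2, 3, 4 this is 6, 5, 4, 3. Section 4.5 says "lapses of product use on one or two assigned nights will be accommodated", so all four cases exceed the allowance and rest on the adverse event exemption. For k = 5 or 6, the 2 or 1 missed nights fall within the allowance only if made up with the same gel.

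**The case against.** The strongest reply is that the protocol already protects this man by other routes. If the clinician links his symptom to the gel, he is told to wash it off and come in. The Investigator only recommends. The man may leave at any time, and the Investigator may withdraw him. Section 4.6 brings in the Protocol Clarifications Team on whether a man who has discontinued should continue or cross over, and Section 10.1 gives that team adverse event management questions. The study-specific procedures manual covers adverse event management and is not shown, so it may contain severity guidance.

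Most of this stands, and it limits the point. A reader might infer that the protocol has no severity trigger for individuals at all. It does: Appendix III grades signs, continuing for questionable erythema, stopping the current product for definite erythema, and ending participation for vesicles, bullae or ulcers. A reader might also infer that a man in severe pain cannot be taken off the gel without breaching the protocol. Sections 3.4 and 4.6 are protocol provisions, and using them is no deviation.

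The reply does not remove the row itself. These safeguards are discretionary and carry no symptom grade, while the table to which the recommendation is tied says to continue.

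On adherence, Section 4.6 speaks to men who discontinue for an adverse event without limiting this to discontinuations that Appendix III requires, and the reference in Section 4.5 may be a mere pointer. That largely answers the question. What remains is a mismatch of wording, not a rule that such a man must be withdrawn.

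**Conclusion.** The point holds in a limited form. For sign-free symptoms of any grade, Appendix III makes continued dosing the default, and the protocol sets no symptom grade for stopping. Sign-based stops and discretionary safeguards reduce the risk. The case is probably rare: 0 to 1.5 of 72 product-use periods, resting on symptom rates carried over from HIV-uninfected men and on an assumed grade 3 share of 0% to 10%. The range includes zero. How the DAIDS table grades penile itching or burning cannot be checked, because that table is in the procedures manual.

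A reader might infer that the primary results would be distorted. The protocol does not support that: Sections 4.5 and 7.6 keep all enrolled men in the tabulations, so the event is counted whether he continues, stops or is replaced. No sample size or probability figure changes. This is a cheap safety improvement that should be made.

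**What to change.** Make three edits.

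1. In the irritative-symptoms row of Appendix III, limit continuation to sign-free symptoms of grade 1 or 2, and allow discontinuation on clinical judgement, as the row for other epithelial change already does.
2. Add a line: for grade 3 or higher symptoms judged possibly, probably or definitely related, stop the current product, re-examine within 3 days, and consider the man for crossover to the next product.
3. In Section 4.5, extend the adverse event exemption to any discontinuation for an adverse event that Appendix III requires or the Investigator recommends. This matches Section 4.6 and also covers a man who stops for persistent grade 2 symptoms, whom a grade 3 line alone would leave unclear.

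The cost is one changed row, one new line and one sentence, with the amendment approvals in Section 10.3. Grading is already required by Section 6, and relatedness is already judged for the Section 7.5 rule, so no new procedure is needed. The downside is that a few men may receive fewer than seven doses of a gel.
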